8. SECONDARY STATISTICAL ANALYSES

8.1. Safety Analyses

8.1.1. Overview of Planned Analyses

The safety analyses will be based on the Safety population, unless otherwise specified.

[Table 6](#) provides an overview of the planned analyses, with full details of data displays being presented in [Appendix 11](#): List of Data Displays.

Table 6 Overview of Planned Safety Analyses

Endpoint	Absolute				Change from Baseline			
	Summary		Individual		Summary		Individual	
	T	F	F	L	T	F	F	L
Exposure								
Exposure	Y			Y				
Adverse Events								
All AE's	Y			Y				
Serious AE's				Y				
Drug Related AEs	Y			Y ¹				
Withdrawal AE's	Y			Y				
Relationship Between System Organ Class and Verbatim Text				Y				
Liver Event				Y				
Laboratory Values								
Clinical Chemistry	Y			Y ²				
Hematology	Y			Y ²				
Clinical Lab Reference Ranges				Y				
Treatment Emergent Toxicity Grade	Y							
Urinalysis	Y			Y				
ECG's								
ECG Findings	Y			Y				
ECG Values	Y			Y ²	Y			
Category of QTc Data	Y				Y			
ECG Values Outside the PCI Range				Y				
Vital Signs								
Vitals Values	Y			Y ²	Y			
Vital Signs Measurements Outside the PCI Range				Y				

NOTES :

- T = Table, F = Figures, L = Listings, Y = Yes display generated.
- Summary = Represents TFL related to any summaries (i.e. descriptive statistics) of the observed raw data.
- Individual = Represents FL related to any displays of individual subject observed raw data.
 - 1: Part of all AEs listing
 - 2: Listing will include toxicity grade or flag for H/L if out of normal range

10. APPENDICES

Section	Appendix
RAP Section 4: Analysis Populations	
Section 10.1	Appendix 1: Protocol Deviation Management
RAP Section 5 : General Considerations for Data Analyses & Data Handling Conventions	
Section 10.2	Appendix 2: Data Management
Section 10.3	Appendix 3: Time and Events
Section 10.4	Appendix 4: Treatment States & Phases
Section 10.5	Appendix 5: Data Display Standards & Handling Conventions 
 • Study Treatment & Sub-group Display Descriptors • Baseline Definitions & Derivations • Reporting Process & Standards
Section 10.6	Appendix 6: Derived and Transformed Data 
 • General • Study Population • Safety • Pharmacokinetic
Section 10.7	Appendix 7: Premature Withdrawals & Handling of Missing Data 
 • General • Study Population & Safety
Section 10.8	Appendix 8: Values of Potential Clinical Importance 
 • Laboratory Values • ECG • Vital Signs
Section 10.9	Appendix 9: Model Specifications for Statistical Analyses
Other RAP Appendices	
Section 10.10	Appendix 10: Abbreviations & Trade Marks
Section 10.11	Appendix 11: List of Data Displays
Section 10.12	Appendix 12: Example Mock Shells for Data Displays

10.1. Appendix 1: Protocol Deviation Management

10.1.1. Exclusions from PK Parameter Summary Population

All protocol deviations will be reviewed, and only the important deviations will be listed and summarized. Some subjects may be excluded from analysis due to protocol deviations. A subject meeting any of the following criteria will be excluded from the PK Parameter Summary Population:

Number	Exclusion Description
01	Failure of any inclusion/exclusion criteria, but subject is still enrolled
02	A subject with emesis occurring within 4 hours of the dose on Day 14 or Day 28
03	A subject who does not have evaluable PK parameters from both periods
04	A subject who has not dosed correctly on the days for PK collections

10.2. Appendix 2: Data Management

10.2.1. Data Format and Process

Data Type	Source	Format of Data	Planned Date of Final File	Responsibility
Safety	PIMS>SI data	SI>STDM	DBF	Accenture
PK Concentration	SMS2000 data file	dat file	DBF	BIB/BESM
PK Concentration (ADPC), WNL File	PK concentration data (SDTM PC), exposure (EX) and demography (DM) datasets ²	ADaM, CSV file	DBF + 5 Days ¹	QSci
PK Parameters	WNL file	CSV file	PK Concentration, WNL file + 10 Days	CPMS

1. Provided SDTM PC, EX and DM are in time and clean
2. PK concentration data is released via SMS2000 by Bioanalysis, Immunogenicity and Biomarkers (BIB)/Bioanalytical External Study Monitors (BESM) and the SDTM PC contains date/times and PK sample ID

CONFIDENTIAL

205712

Procedure	Screen ¹	Day -1	Treatment Period 1 Day													Treatment Period 2 Day													Early Withdrawal / Follow-up ~10-14 days		
			1	2	3	4	5	6	7	8	9	10	11	12	13	14	15	16	17	18	19	20	21 ²	22	23	24	25	26 ²		27	28
Safety Laboratory assessments	X	X												X														X			X
12-lead ECG ⁶	X		X												X														X		X
Vital signs (Including Temperature) ⁶	X		X												X							X							X		X
Administer CAB 30 mg once daily ⁷			X	X	X	X	X	X	X	X	X	X	X	X	X	X	X	X	X	X	X	X	X	X	X	X	X	X	X		
Administer RBT 300 mg once daily ⁷																X	X	X	X	X	X	X	X	X	X	X	X	X			
Dispense CAB ⁸			X																												
Dispense CAB ⁹ and RBT ¹⁰																X															
Pharmacokinetic Sampling ¹¹														X	X	X											X	X	X	X	
Admit to Unit		X												X														X			
Discharge from Unit			X													X													X		
Outpatient Visit	X																					X					X			X	

Procedure	Screen ¹	Day -1	Treatment Period 1 Day													Treatment Period 2 Day							Early Withdrawal / Follow-up ~10-14 days									
			1	2	3	4	5	6	7	8	9	10	11	12	13	14	15	16	17	18	19	20		21 ²	22	23	24	25	26 ²	27	28	29
Drug accountability													X									X				X	X					
Genetic sample ¹²			←-----→																													
SAE Review	←-----→																															
AE Review	←-----→																															
Concomitant medication review	←-----→																															

CONFIDENTIAL

205712

1. Screening must be performed within 30 days prior to receiving the dose of CAB on Day 1.
2. Day 21 and Day 26 is an outpatient visit.
3. An ocular assessment will be performed only for subjects who experience eye symptoms.
4. A brief symptom directed physical exam will be completed as needed.
5. A serum pregnancy test will be performed at the screening visit and a urine pregnancy test at all other time points specified.
6. Duplicate ECG, BP, and HR assessments will be conducted pre-dose on Day 1. Single measurements will be collected at all other time points.
7. Study medication will be administered with 240 mL of water within the unit on Days 1, 13, 14, 15, 21, 26, 27, and 28. Dosing on non-PK days may be with or without food, but dosing on serial PK days (Day 14 in Period 1 and Day 28 in Period 2) must be after an overnight fast of at least 6 hours, and no food will be allowed for 4 hours after dosing on these serial PK days.
8. Dispense the bottle of CAB tablets to the subject on Day 1 to receive CAB dosing at home on Days 2 to 12 in Period 1
9. Dispense the bottle of CAB tablets to the subject on Day 15 to receive CAB dosing at home on Days 16 to 20 and Days 22 to 25 in Period 2; dosing on Day 21, 26, 27, and 28 is in the unit.
10. Dispense the bottle of RBT capsules to the subject on Day 15 to receive RBT dosing at home on Days 16 to 20 and Days 22 to 25 in Period 2; dosing on Day 21, 26, 27, and 28 is in the unit.
11. Plasma PK samples (2 mL of blood per sample) will be collected to measure CAB at the following time points: Period 1: predose (within 15 minutes prior to dose) on Day 13; and pre-dose (within 15 minutes prior to dose), 1, 2, 3, 4, 8, 12, and 24 hours after CAB dosing on Day 14. Period 2: pre-dose (within 15 minutes prior to dose) on Days 26 and 27 and pre-dose (within 15 minutes prior to dose) on Day 28 and, 1, 2, 3, 4, 8, 12, and 24 hours after CAB +RBT dosing on Day 28.
12. It is recommended that the Pharmacogenetic sample be collected on Day 1, but it may be collected at any time following administration of investigational product.

10.4. Appendix 4: Treatment States and Phases

10.4.1. Treatment State and Study Phases

Assessments and events will be classified according to the time of occurrence relative to study visit or the start and/or stop date/time of the study treatment.

Treatment State	Study Phase
Pre-Treatment	Screening assessments collected prior to the Day 1 visit
On-Treatment	Period 1 and Period 2
Follow-up	Follow-up Visit

10.4.1.1. Treatment States for AE, SAE and Concomitant Medications Data

Treatment State	Definition
Screening	AE(SAE or conmed) Start Date/Time < Study Treatment Start Date/Time. Based on the protocol, these AEs and concomitant medications prior to dosing will not be collected in database, and only record in the source document, but SAE will be captured on the dataset
Treatment A	If AE (SAE or conmed) onset date/time is on or after Period 1 treatment start date/time & before Period 2 treatment date/time Study Period 1 Treatment Start Date/Time ≤ AE Start Date/Time < Study Period 2 Treatment Date/Time]
Treatment B	If AE (SAE or conmed) onset date/time is on or after Period 2 treatment start date/time & before Study Conclusion date/time Study Period 2 Treatment Start Date/Time ≤ AE Start Date/Time < Study follow-up visit Date/Time]
Follow-up	All unsolved AEs (SAE or conmed) during the follow-up will be associated with the treatment from Period 2, and no AEs (SAE or conmed) will be report under the follow-up
Onset Time Since First Dose (Days)	If Treatment Start Date/Time > AE Onset Date/Time = AE Onset Date - Treatment Start Date If Treatment Start Date/Time ≤ AE Onset Date/Time = AE Onset Date - Treatment Start Date +1 Missing otherwise
Duration (Days)	AE Resolution Date – AE Onset Date + 1
Drug-related	If relationship is marked 'YES' on eCRF

NOTES:

- If the study treatment stop date is missing then the AE will be considered to be On-Treatment.

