3. OBJECTIVES AND ENDPOINTS

Primary	

 To compare steady state CAB exposure following 30 mg oral dose once daily with and without RBT 300 mg once daily. 	
 Plasma CAB_AUC(0-τ), C_{max}
Secondary	

 To describe the pharmacokinetic (PK) of CAB 30 mg oral dose once daily administered alone and co-administered with RBT. 	
 Plasma CAB_Cτ, t_{max}, t_{1/2}, CL/F

 To assess the safety and tolerability of CAB 30 mg oral dose administered alone and in combination with RBT 300 mg once daily. 	
 Safety and tolerability parameters, including adverse events, concurrent medication, clinical laboratory screens, electrocardiogram (ECG), and vital signs assessments.

AUC_(0-t) = area under the plasma concentration time curve from time zero to the last quantifiable time point C_{max} = maximum observed concentration C_t = last quantifiable concentration t_{max} = time of maximum observed concentration t_{1/2} = the elimination half-life
 
 CL/F = apparent oral clearance 	

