 8. Any other medical condition which, in the judgment of the investigator and medical monitor, could jeopardize the safety of the subject or the integrity of the data derived from that subject. This includes but is not limited to any pre-existing condition that interferes with normal gastrointestinal anatomy or motility that could interfere with the absorption, metabolism, and/or excretion of the study drug.

CONCOMITANT MEDICATIONS

9. Unable to refrain from the use of prescription or non-prescription drugs, including vitamins, herbal and dietary supplements (including St John's Wort) within 7 days (or 14 days if the drug is a potential enzyme inducer) or 5 half-lives (whichever is longer) prior to the first dose of study medication, unless in the opinion of the Investigator and Viiv Medical Monitor the medication will not interfere with the study procedures or compromise subject safety. See Section 6.10.2 for concomitant medications that are prohibited for this study.

RELEVANT HABITS

10. History of regular alcohol consumption within 6 months of the study defined as an average weekly intake of >14 drinks. One drink is equivalent to 12 g of alcohol, 12 ounces (360 mL) of beer, 5 ounces (150 mL) of wine or 1.5 ounces (45 mL) of 80 proof distilled spirits.
11. A history of regular use of tobacco, or nicotine-containing products within 30 days prior to screening.

CONTRAINDICATIONS

12. History of sensitivity to any of the study medications, or components thereof or a history of drug or other allergy that, in the opinion of the investigator or Medical Monitor, contraindicates their participation.

DIAGNOSTIC ASSESSMENTS AND OTHER CRITERIA

13. Presence of Hepatitis B surface antigen (HBsAg) positivity at screening or within 3 months prior to first dose of study treatment. Positive Hepatitis B core antibody (HBcAb) with negative hepatitis B surface antibody should also be excluded.
14. Positive Hepatitis C antibody test.
15. A positive pre-study drug/alcohol screen.
16. A positive test for HIV antibody.
17. A positive QuantiFERON Gold test or clinical evidence of tuberculosis (TB) infection.
18. Where participation in the study would result in donation of blood or blood products in excess of 500 mL within a 56 day period.

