6.10.2. Prohibited Medications and Non-Drug Therapies

Subjects must abstain from taking prescription or non-prescription drugs (including vitamins and dietary or herbal supplements), within 7 days (or 14 days if the drug is a potential enzyme inducer) or 5 half-lives (whichever is longer) prior to the first dose of study medication until completion of the follow-up visit, unless in the opinion of the Investigator and sponsor the medication will not interfere with the study.

Use of antacids, vitamins and iron supplements are strictly prohibited within 7 days (or 14 days if the drug is a potential enzyme inducer) or 5 half-lives (whichever is longer) prior to the first dose of study medication and for the duration of the trial.

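### SAP 10.4.1.1 assigns concomitant medications to a treatment by onset and omits those begun before dosing, which misstates concurrent medication by treatment but leaves the primary ratio untouched

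*SAP*

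**What the plan says.** SAP 10.4.1.1 is a single table covering adverse events, serious adverse events and concomitant medications. Four of its rows matter here.

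- Screening row: "AE(SAE or conmed) Start Date/Time < Study Treatment Start Date/Time". For this state, "these AEs and concomitant medications prior to dosing will not be collected in database, and only record in the source document". Serious adverse events are the exception and are kept.
- Treatment A row: "If AE (SAE or conmed) onset date/time is on or after Period 1 treatment start date/time & before Period 2 treatment date/time".
- Treatment B row: "If AE (SAE or conmed) onset date/time is on or after Period 2 treatment start date/time & before Study Conclusion date/time".
- Follow-up row: "All unsolved AEs (SAE or conmed) during the follow-up will be associated with the treatment from Period 2". The row adds that nothing is reported under follow-up as a separate state.

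The Screening, A and B rows use no stop date, and no row places a medication in every period that it spans. The Duration row is defined from adverse event dates only.

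The protocol lets medicines continue. Exclusion criterion 9 (Protocol 5.2) bars them "unless in the opinion of the Investigator and Viiv Medical Monitor the medication will not interfere with the study procedures or compromise subject safety", and Protocol 6.10.2 bars them "unless in the opinion of the Investigator and sponsor the medication will not interfere with the study". Protocol 6.10.1 allows acetaminophen (up to 2 g/day) throughout and other drugs case by case.

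Protocol 3 lists the secondary safety endpoint as "Safety and tolerability parameters, including adverse events, concurrent medication, clinical laboratory screens" and further items, assessed for CAB alone and for the combination. Protocol 9.4 says that listings note the treatment and that summaries are given by treatment.

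**The concern.** An adverse event is reasonably attributed to the treatment in force when it began. A medicine is an exposure, and the useful question is which periods it was taken in. Start time alone does not answer that in a fixed-sequence design with no washout, where anything continued from Period 1 runs straight into Period 2.

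Two things are at stake. The first is the by-treatment account of concurrent medication, which can understate use during the combination period and omit long-term medicines that were waived in. The second is interpretation. If one subject has an unusual ratio, a reader will look at what else that subject was taking, and a medicine begun before Day 1 would not be in the dataset to be found.

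**Working it through.** The plan gives no figure on this point, so the check applies the SAP rows to example courses.

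**Inputs.** First dose is on Day 1 and the first Period 2 dose on Day 15. The serial PK days are Day 14 and Day 28 (SAP 10.3, Time and Events footnotes). Follow-up is about 10 to 14 days after the last CAB dose, that is Day 28 + 10 = Day 38 to Day 28 + 14 = Day 42. The courses are illustrations; the documents give no co-medication data.

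| Medication taken | Day 14 profile | Day 28 profile | State under SAP 10.4.1.1 |
|---|---|---|---|
| Day -5 to Day 30 | yes | yes | Screening; not in the database |
| Day 3 to Day 29 | yes | yes | Treatment A only |
| Day 10 to Day 28 | yes | yes | Treatment A only |
| Day 14 to Day 28 | yes | yes | Treatment A only |
| Day 3, ongoing at follow-up | yes | yes | Treatment A by onset; Period 2 by the Follow-up row |
| Day 3 to Day 20 | yes | no | Treatment A only |
| Day 16 to Day 29 | no | yes | Treatment B |

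**General result.** A medicine taken on both PK days must have started by Day 14, before the Day 15 dose. The onset rows therefore can never place it under Treatment B. Only the Follow-up row can, and only if the medicine is still in use at Day 38 to 42.

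**Size in days.**

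- Day 10 to 28: Days 10-14 are 5 days in Period 1 and Days 15-28 are 14 days in Period 2. Under B, 0 of the 14 are counted.
- Day 3 to 20: Days 15-20 are 6 days in Period 2, of which 0 are counted.
- Started before Day 1 and taken throughout: 14 + 14 = 28 dosing days, of which 0 are in the database.

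**Basis for the pre-dose omission.** The SAP row attributes it to the protocol. Protocol 7.3.1.1 limits the collection of adverse events to the time from the start of treatment, but says nothing about medications that began earlier and continue. Protocol 7.2 has medication history assessed at screening, and Protocol 8 has concomitant medications coded as trial data. I found no protocol text that excludes an ongoing medicine from the CRF.

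**Effect on the primary analysis.** The model in SAP 7.2 and 10.9.1 has treatment as a fixed effect and subject as a random effect, with no medication term. None of the four exclusion rules in SAP 10.1.1 uses the medication state. Relabelling a medication therefore changes neither the geometric mean ratio nor its 90% CI. A medicine that multiplies a subject's exposure by the same factor f on Day 14 and Day 28 also drops out of that subject's contrast: ln(f x B) - ln(f x A) = ln B - ln A.

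**The case against.** The strongest reply is that the practical damage is small. Most medicines are barred from before dosing until follow-up, and those waived in have been judged not to interfere. The main planned outputs are by-subject listings for about 15 subjects (SAP 10.11.3, Table 1.6, and ICH Listing 7). SAP 10.7.2.1 implies that listings carry dates, so the overlap of an on-study medicine could probably be read there whatever its treatment label. Individual treatment ratios are listed as well (Table 3.4), so the two can be compared by subject.

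Much of this stands for medicines started after first dose. It does not help those started before, which are absent from any listing drawn from the database. Nor does it protect a summary by treatment, which the SAP triggers on two different conditions: more than 10 records in Table 3, and a listing longer than 3 pages in 10.11.3.

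Three stronger readings are tempting, and the documents do not support them.

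- *That the primary ratio is biased.* The labels do not enter the model, and a stable effect on both PK days largely cancels. The documents give no effect size for any co-medication, so no shift can be attributed to this rule.
- *That washout compliance cannot be checked, or that prohibited use goes unhandled.* The washout is part of exclusion criterion 9. Eligibility deviations are taken from the eCRF page and listed (SAP 4.1; Listing 4), and failing a criterion removes the subject from the PK summary population (SAP 10.1.1, rule 01). Prohibited use on study is a protocol deviation, and SAP 4.1 requires deviations that could lead to PK exclusion to be categorised before the database freeze. Only the line-level medication detail is missing.
- *That labelling a medicine first taken after the last dose as Treatment B is an error.* The SAP states this convention openly and applies it to adverse events too.

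**Conclusion.** The point holds as a defect in classification and data capture. The onset rows give a wrong treatment label to a medicine started in Period 1, taken through Day 28 and stopped before follow-up. The Treatment A and Follow-up rows conflict for one still ongoing at follow-up. A permitted medicine ongoing at Day 1 is left out altogether. Its size is up to 14 of 14 combination-period days uncounted for a carried-over medicine, and 28 of 28 dosing days for one taken throughout. How many subjects would be affected cannot be known from the documents; with use restricted, it may be few.

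The consequence is confined to the concurrent-medication part of the secondary safety endpoint and to the interpretation of outlying individual ratios. The primary geometric mean ratio and its CI do not move.

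This rests on two assumptions: that summaries of medication are by treatment, as Protocol 9.4 says, and that the protocol has no separate rule excluding earlier medicines. The Time and Events grid cannot be read reliably enough to settle when medication review begins, so I place no weight on it.

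**What to change.** In SAP 10.4.1.1, give concomitant medications their own rule, separate from adverse events:

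1. Count each medication under every treatment period that its start-to-stop interval overlaps.
2. Reconcile the Treatment A and Follow-up rows, so that a medicine started in Period 1 and still ongoing at follow-up has one unambiguous treatment assignment.
3. Record in the CRF every medication ongoing at Day 1, and remove the sentence that leaves these in source documents only.
4. State how a missing or partial stop date is treated for the overlap rule, because SAP 10.7.2.1 gives date conventions for adverse events only.

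The cost is a short SAP edit and a few extra CRF lines for about 15 subjects. The information is already assessed at screening and held in source documents, so no new assessment is needed. A medication counted in both periods means that by-treatment counts will not add up to the overall count; a footnote covers that. The PK model and the PK populations need no change.

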4.2. Treatment Periods and Duration

Subjects will undergo a screening visit within 30 days of the first dose of study drug, followed by two treatment periods and a follow-up period.

Subjects will undergo clinical safety assessments and serial PK assessments at time-points specified in Section 7.1, Time and Events table of the protocol.

Period 1

Eligible participants will be admitted to the unit on Day -1.

On Day 1, following completion of the required pre-dose measurements, the investigator or authorized study unit personnel will administer a single oral dose of 30 mg CAB to each subject in the unit.

Subjects will be dispensed a bottle of CAB to be taken at home on Days 2-12 and discharged from the unit. Subjects will be provided with a subject diary to document daily recordings of dosing occurring outside of the unit. Subjects will be re-admitted to the unit in the morning on Day 13. Prior to dosing, a CAB PK sample will be obtained, and then the subjects will receive a single 30 mg dose of CAB on Day 13 and remain in the unit overnight. On Day 14, following an overnight fast of at least 6 hours, subjects will receive a single 30 mg dose of CAB with serial CAB PK samples collected pre-dose and through 24 hours after dosing up to Day 15. There will be no washout between Period 1 and Period 2.

Period 2

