On Day 15 following the completion of the required Day 14 safety assessments and PK collection, subjects will proceed to Period 2, where site staff will administer a single dose of RBT 300 mg and a single dose of CAB 30 mg in the unit. Subjects will be discharged and dispensed a bottle of RBT and a bottle of CAB to be taken at home on Days 16-20. Subjects will be provided with a subject diary to document daily recordings of home dosing. In the morning of Day 21, subjects will bring their bottle of RBT and bottle of CAB for observed dosing in the unit and safety assessments as an outpatient visit. Following these procedures, subjects will be discharged with their supply of CAB and RBT and instructed to take their daily doses of study medications at home in the mornings of Days 22 through 25. On Day 26, subjects will return to the unit for a pre-dose PK collection and observed dosing as an outpatient visit and then be discharged home. On Day 27, subjects will be re-admitted to the unit for a pre-dose PK collection, observed dosing, and safety assessments then remain in the unit overnight. In the morning of Day 28 following an overnight fast of at least 6 hours, subjects will receive a single dose of RBT and a single dose of CAB in the unit with serial CAB PK samples collected pre-dose and through 24 hours after dosing up to Day 29. Subjects will be discharged from the unit on Day 29 after the final assessment is completed. Subjects will complete a follow-up visit ~ 10-14 days after the last 30 mg oral dose of CAB.

At the follow-up visit, laboratory safety assessments (including pregnancy test for females of childbearing potential) will be performed, and vital signs together with a 12-lead ECG will be obtained.

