10.11.4. Safety Tables

Safety Tables					
No.	Population	IDSL / TST ID / Example Shell	Title	Programming Notes	Deliverable [Priority]
Adverse Events					
2.1.	Safety	LAI117010/ Table 2.1	Summary of Exposure Data	By subject and treatment	SAC
2.2.	Safety	LAI117010/ Table 2.2	Relationship of Adverse Event System Organ Classes, Preferred Terms, and Verbatim Text		SAC
2.3.	Safety	LAI117010/ Table 2.3	Summary of All Adverse Events by Treatment		SAC
2.4.	Safety	LAI117010/ Table 2.4	Summary of Drug-Related Adverse Events by Treatment		SAC
2.5.	Safety	LAI117010/ Table 2.5	Listing of Serious Adverse Events	By subject and treatment.	SAC
2.6.	Safety	LAI117010/ Table 2.6	Listing of Adverse Events Leading to Permanent Discontinuation of Study Drug or Withdrawal from Study	By subject and treatment	SAC
Labs					
2.7.	Safety	LAI117010/ Table 2.7	Listing of Reference Ranges for Clinical Laboratory Tests		SAC
2.8.	Safety	LAI117010/ Table 2.8	Summary of Clinical Haematology Laboratory Data by Treatment and Time		SAC
2.9.	Safety	LAI117010/ Table 2.9	Summary of Clinical Chemistry Laboratory Data by Treatment and Time		SAC
2.10.	Safety	LAI117010/ Table 2.10	Summary of Treatment Emergent Grade 2 or Higher Lab Abnormalities by Treatment	Summary of Treatment Emergent Lab toxicity only.	SAC
2.11.	Safety	LAI117010/ Table 2.11	Listing of Treatment Emergent Grade 2 or Higher Lab Abnormalities	By subject and treatment	SAC
2.12.	Safety	CP_LB5	Summary of All Urinalysis Data		SAC

Safety Tables					
No.	Population	IDSL / TST ID / Example Shell	Title	Programming Notes	Deliverable [Priority]
Vital Signs					
2.13.	Safety	LAI117010/ Table 2.13	Summary of Vital Signs by Treatment and Time	Include BP and HR only.	SAC
2.14.	Safety	LAI117010/ Table 2.14	Summary of Change from baseline in Vital Signs by Treatment and Time	Include BP and HR only.	SAC
2.15.	Safety	LAI117010/ Table 2.15	Listing of Vital Signs for Subjects with Abnormalities of Potential Clinical Importance	By subject and treatment	SAC
ECGs					
2.16.	Safety	LAI117010/ Table 2.16	Summary of ECG Findings		SAC
2.17.	Safety	LAI117010/ Table 2.17	Summary of ECG Values by Treatment and Time		SAC
2.18.	Safety	LAI117010/ Table 2.18	Summary of Change from Baseline in ECG Values by Treatment and Time		SAC
2.19.	Safety	LAI117010/ Table 2.19	Summary of Category of QTc Data by Treatment and Time		SAC
2.20.	Safety	LAI117010/ Table 2.20	Summary of Category of QTc Change from Baseline by Treatment and Time		SAC

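### The by-treatment AE tables count 14 days for CAB alone but 23–27 days for RBT+CAB, so the two columns are not like for like

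*SAP*

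**What the plan says.** SAP 10.4.1.1 sorts AEs, SAEs and concomitant medications into treatment states by onset time.

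- **A (CAB alone)** is assigned by this rule: "If AE (SAE or conmed) onset date/time is on or after Period 1 treatment start date/time & before Period 2 treatment date/time".
- **B (RBT+CAB)** is assigned by this rule: "If AE (SAE or conmed) onset date/time is on or after Period 2 treatment start date/time & before Study Conclusion date/time". The formula beneath gives the upper limit as "AE Start Date/Time < Study follow-up visit Date/Time".
- **Follow-up:** unresolved events are attached to the Period 2 treatment, and "no AEs (SAE or conmed) will be report under the follow-up".

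Protocol 4.2 sets the dates. Period 2 dosing starts on Day 15 with no washout, the last dose is on Day 28, and "Subjects will complete a follow-up visit ~ 10-14 days after the last 30 mg oral dose of CAB".

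SAP 10.11.4 plans Table 2.3, "Summary of All Adverse Events by Treatment", and Table 2.4, the same display for drug-related events. The visible text plans no person-time denominator, common window or on-dosing-only AE summary.

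Elsewhere the SAP keeps follow-up apart. Section 10.4.1 lists it as its own treatment state, and 10.4.1.2 gives it its own slice for the other safety data, with Period 2 limited to Days 15–28. Section 10.5.1 describes Treatment B as a 14-day regimen.

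**The concern.** Assessing safety and tolerability of CAB alone and in combination with RBT is a secondary objective, and Tables 2.3 and 2.4 are its by-treatment AE summaries. A reader who sees two columns side by side will compare them. One column counts onsets over the dosing period only. The other counts onsets over the dosing period plus the whole follow-up.

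Nothing visible on the page would signal this. Both regimens are described as lasting 14 days. The exposure formula in SAP 10.6.2 (stop date minus start date plus 1) gives 14 days on each treatment for a subject who completes both. A difference produced by observation time could then be read as an effect of adding rifabutin.

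**Working it through.** The plan states no length for either AE window, so there is no figure to reproduce directly. The planned subject numbers matter for the counts below and do reproduce: 12 / (1 − 0.20) = 15 (Protocol 9.2.1).

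**Window lengths** (Protocol 4.2 dates with the SAP 10.4.1.1 rules, for a subject who completes both periods):

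- A: Day 1 dose to Day 15 dose = 15 − 1 = 14 days.
- B: Day 15 dose to the follow-up visit on Day 28 + 10 to 28 + 14, i.e. Day 38 to 42 = 23 to 27 days.
- Ratio B/A: 23/14 = 1.64 to 27/14 = 1.93.
- Part of B after the last 24-hour dosing interval (Day 29 onward): 23 − 14 = 9 to 27 − 14 = 13 days, or 9/23 = 39% to 13/27 = 48% of the window.

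**Effect on the proportion of subjects with an AE.** The documents give no AE rate, so what follows is an assumption: a constant daily rate, equal in both periods and in follow-up. Then p_B = 1 − (1 − p_A)^(L_B/14).

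| 14-day risk, A | B, 23 days | B, 27 days |
|---|---|---|
| 20% | 31% | 35% |
| 30% | 44% | 50% |

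**Lower rate in follow-up.** Let f be the follow-up rate as a fraction of the on-dosing rate. The ratio of expected AE onsets per subject is (14 + f × (L_B − 14)) / 14:

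| f | B, 23 days | B, 27 days |
|---|---|---|
| 1 | 1.64 | 1.93 |
| 0.5 | 1.32 | 1.46 |
| 0.25 | 1.16 | 1.23 |
| 0 | 1.00 | 1.00 |

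**Effect of withdrawals.** Suppose all 3 expected withdrawals occur before Period 2.

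- Subject-days are 15 × 14 = 210 for A and 12 × 23 to 12 × 27 = 276 to 324 for B, a ratio of 1.31 to 1.54.
- At a 30% 14-day risk, the expected subjects with an AE are 15 × 0.30 = 4.5 under A and 12 × 0.443 to 12 × 0.497 = 5.3 to 6.0 under B. With no withdrawals, B would have 6.7 to 7.5.
- At f = 0.25, the ratio of raw event counts is 0.8 × 1.16 to 0.8 × 1.23 = 0.93 to 0.99, so the total count in B need not be higher.

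**One trial.** With equal daily rates and Poisson counts, the simulated chance that B shows more AEs than A is 57–78% when 3 AEs are expected in A, and 71–95% when 10 are expected. The ranges cover 12 or 15 subjects in B and follow-up at 10 or 14 days.

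**Drug still present after dosing.** Protocol 4.5 gives half-lives of about 40 h (CAB) and 38 h (RBT). Five half-lives are 5 × 40/24 = 8.3 days and 5 × 38/24 = 7.9 days.

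**With the proposed windows.** A = 14 days and B = Day 15 dose to Day 29 = 14 days. The ratio is 1.00, and equal rates give equal expected incidence.

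**The case against.** The strongest defence is that the rule is a deliberate and cautious attribution. A reader might infer that follow-up is drug-free and that late events do not belong to Treatment B. The documents do not support that: follow-up is off-dosing, but both drugs are still clearing for roughly 8 of its 10–14 days. Protocol 4.6.2 also notes that uveitis can appear from 2 weeks after rifabutin is started, which here is Day 29 or later. This stands, and it is why no late event should be dropped.

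A reader might also infer that RBT+CAB is bound to show more AEs. That goes too far. The excess is in expected incidence, exists only if AEs start in follow-up, and is not certain in 12–15 subjects. Table 2.4 is further limited to events the investigator judges drug-related, so a constant background rate fits it less well.

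Other parts of the defence also stand:

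- Safety is summarised descriptively, with no formal AE contrast.
- SAP 10.4.1.1 derives onset time since first dose, and Listing 10 shows every AE, so a careful reader could separate late onsets.
- Different handling in 10.4.1.2 is not a contradiction in itself, since it concerns measurements taken at visits.
- Tables 2.3 and 2.4 follow shells from an earlier study that are not reproduced, so a clarifying footnote cannot be ruled out.
- The fixed sequence confounds treatment with period, and matching windows does not remove that. The difference in visit schedule between periods is likewise left unchanged, so it forms no part of this point.

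What the defence does not answer is that the summary columns rest on unequal observation time and no visible text says so.

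**Conclusion.** The point holds as a minor display issue. The window lengths (14 against 23–27 days, ratio 1.64–1.93) follow directly from the documents. The size of any distortion does not, because no AE rate is given. Under an equal constant rate, a 20% risk becomes 31–35%. The ratio of expected onsets per subject is 1.32–1.46 if the follow-up rate is half the on-dosing rate, 1.16–1.23 at a quarter, and 1.00 if nothing starts in follow-up. Assigning late AEs to Treatment B is a defensible attribution but does not give a like-for-like comparison. The primary PK analysis is unaffected.

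**What to change.** Amend SAP 10.4.1.1, including its Follow-up row, and Tables 2.3 and 2.4, before the database is frozen:

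1. Show Treatment B AEs with onset from the first Period 2 dose to 24 hours after the last Period 2 dose (14 days for completers).
2. Show later onsets in a separate column, for example 'Follow-up (after RBT+CAB)', in line with the separate follow-up state in SAP 10.4.1.
3. Keep a combined 'B including follow-up' column, so that late events remain visible against the last treatment.
4. Footnote the number of subjects and subject-days for each column.

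The cost is SAP wording and one or two extra columns in two descriptive tables. No new data are needed and AE collection does not change. The on-dosing B column will show fewer events than now planned; the combined column covers that.
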